3. ENDPOINTS AND BASELINE VARIABLES: DEFINITIONS AND CONVENTIONS

3.1. Primary Endpoints

3.1.1. Zavegepant PK Concentrations

Venous blood and Tasso PK samples will be collected according to the SoA given in the protocol. For each individual, blood to plasma (B/P) ratios will be calculated by dividing concurrent (i.e. Day 1, 1 hour and 8 hour post-dose) whole blood zavegepant concentrations with the plasma zavegepant concentrations. The plasma equivalent zavegepant concentration by microsampling using the Tasso-M20 will be calculated by dividing with the individual B/P ratio. For the Tasso-Plus, normalization of the zavegepant concentration is not needed.

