A healthy participant population is considered for the study because healthy participants with no concomitant diseases and using no concomitant medications represent a homogenous population allowing for proper evaluation of the PK, safety, and tolerability of a drug without confounding factors. Six PK samples will be collected from the Tasso devices at the same time of collecting venous blood samples, as described in the [SoA, Table 2](#). Those 6 Tasso-venous paired samples collected in 7 participants for each device ($7 \times 6 = 42$ data points) are sufficient to meet the scientific community recommendation for having an adequate Tasso-venous phlebotomy PK bridging study.³⁶ Different PK sampling times were selected to cover the concentration-time profile of zavegeptant IN. Of note, blood-to-plasma ratio samples will be aliquoted from the same venous blood draw as specified in the [SoA, Table 2](#). These samples will be crucial for determining the blood-to-plasma ratio value for each participant to convert the dried blood concentrations collected using Tasso-M20 to their equivalent plasma concentrations for adequate comparison between the 2 methods.

If feasible, 4 Japanese participants will be enrolled among the 14 participants planned for this study to determine the PK and safety of zavegeptant IN in this population since there is no PK and safety data available for the use of zavegeptant IN in this population. Leveraging this data will be useful in supporting the development of zavegeptant IN in Japan. However, the recruitment of these Japanese participants will be optional, and the completion of this trial will not require their enrollment.

As noted earlier, data from clinical trials of zavegeptant IN formulation have shown dysgeusia (bad/metallic/bitter taste) as the most common treatment-emergent adverse event following zavegeptant administration (refer to IB). We hypothesize that the mechanism of dysgeusia associated with zavegeptant nasal spray administration relates to the postnasal dripping of residual spray into the oral cavity and contact with the posterior tongue and taste buds, triggering the taste receptor cells. To test this hypothesis and better understand this adverse event (its intensity, onset, and duration), a taste assessment questionnaire will be performed at 1 (immediately after dosing), 5, 10 and 20 minutes after zavegeptant IN administration.

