8.5. Pharmacokinetics

Venous blood samples of approximately 4 mL, to provide approximately 1.5 mL plasma, will be collected for measurement of plasma concentrations of zavege pant as specified in the

SoA. Prior to centrifugation of blood samples collected at the time points specified in the **SoA, Table 2**, a 500 µL portion of the PK blood sample will be aliquoted and used to determine the blood-to-plasma ratio of zavegeptan. Determining the blood-to-plasma ratio will be crucial for converting the dried blood concentrations collected using Tasso-M20 to their equivalent plasma concentrations for adequate comparison between the 2 methods. For Tasso sampling, approximately 100 µL of blood will be collected from participants using the Tasso-M20 devices, while for Tasso-Plus, approximately 300-500 µL of blood will be collected to provide approximately 150 - 200 µL serum into appropriately labeled tubes for the measurement of zavegeptan concentration as specified in the **SoA, Table 2**. Of note, both Tasso and venous PK samples will be collected at the same time. Instructions for the collection and handling of biological samples will be provided in the laboratory manual or by the sponsor. The actual date and time (24-hour clock time) of each sample will be recorded.

All efforts will be made to obtain the samples at the exact nominal time relative to dosing. Collection of samples up to and including 10 hours after dose administration that are obtained within 10% of the nominal time relative to dosing (eg, within 6 minutes of a 60-minute sample) will not be captured as a protocol deviation, as long as the exact time of the collection is noted on the source document and the CRF. Collection of samples more than 10 hours after dose administration that are obtained \leq 1 hour away from the nominal time relative to dosing will not be captured as a protocol deviation, as long as the exact time of the collection is noted on the source document and the CRF. This protocol deviation window does not apply to samples to be collected more than 10 hours after dose administration at outpatient/follow-up visits with visit windows.

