9.5. Sample Size Determination

Approximately 14 evaluable participants will be enrolled (7 for Tasso-Plus and 7 for Tasso-M20). There is no statistical hypothesis for this study. The sample size determination for this study was based on the established scientific recommendation for having 30 to 40 PK data points to ensure adequate comparison between PCS (test) and venous sampling.³⁶ With a sample size of 7 evaluable participants per each Tasso device, and 6 Tasso-venous paired PK samples collected, there will be sufficient PK data points ($7 \times 6 = 42$ data points from each Tasso device) to meet the scientific community recommendation for having an adequate Tasso-venous phlebotomy PK bridging study.

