2.3. Study Design

This is a single-center, Phase 1, non-randomized, open-label, 2-period study in healthy participants to primarily evaluate the correlation of zavegepant concentration from samples collected using Tasso Devices (Tasso-Plus and Tasso-M20) compared to standard venous phlebotomy. This study consists of two periods which will include approximately 14 participants.

In period 1, 50% (n=7) of participants will use Tasso-Plus, while the other 50% (n=7) will use Tasso-M20. All 14 participants will have 6 PK samples collected using the assigned Tasso device simultaneously with collecting venous blood samples at the following time points, 30 minutes, 1, 2-, 4-, 8-, and 12-hour postdose, as described in the SoA, Table 2 (in the protocol). In addition, taste assessments will be performed at time intervals of 1 (immediately after dosing), 5, 10 and 20 minutes after zavegepant IN administration. Also, if feasible, 4 Japanese participants will be enrolled among those 14 participants to evaluate the PK and safety of zavegepant IN in Japanese vs. non-Japanese participants. For Japanese participants, a total of 12 venous blood samples will be collected at the following time points, 0, 15 minutes, 30 minutes, 1, 1.5-, 2-, 3-, 4-, 6-, 8-, 12-, and 24-hour (refer to SoA, Table 2 in the protocol).

In period 2, a butterscotch candy will be given 5 minutes before administering the zavegepant IN study intervention. Taste assessment will also be performed after zavegepant IN administration with a butterscotch candy in period 2. For taste assessment, each participant will record the sensory attributes at timed intervals of 1 (immediately after dosing), 5, 10 and 20 minutes after zavegepant administration in each period.

Healthy participants will be screened within 28 days prior to the first administration of the study intervention to confirm that they meet the participant selection criteria for the study. Eligible participants will be admitted to the CRU on Day -1 and will be confined in the CRU until Discharge on Day 3 (SoA in the protocol), approximately 24 hours after the second dose. Enrolled participants will receive a single IN dose of zavegepant 10 mg (0.1 mL) in each period. PK venous blood samples as well as Tasso PK sampling, using Tasso-Plus and

Tasso-M20, will be collected at specified intervals as per SoA (Table 2) in the protocol for PK assessments.

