The correlations of paired Tasso-Plus versus venous phlebotomy concentrations and paired Tasso-M20 versus venous phlebotomy concentrations will be reported. Furthermore, Bland-Altman plot analysis will be performed for each pair to evaluate the bias and SD of the bias between the mean differences and to estimate an agreement interval within a 95% confidence limit.

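### At 1 h and 8 h (14 of 42 Tasso-M20 pairs) the venous plasma result both converts the M20 value and serves as its reference, so these pairs do not independently test agreement with venous plasma

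*SAP*

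**What the plan says.** **Building the ratio.** SAP 3.1.1 says B/P "ratios will be calculated by dividing concurrent (i.e. Day 1, 1 hour and 8 hour post-dose) whole blood" results by the venous plasma results. Protocol 4.2 adds that "blood-to-plasma ratio samples will be aliquoted from the same venous blood draw". Protocol 8.5 explains that, before centrifugation, a 500 µL "portion of the PK blood sample will be aliquoted and used to determine the blood-to-plasma ratio". The rest of the tube yields the PK plasma, and no separate plasma sample for the ratio is described.

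**Applying it.** SAP 3.1.1: "The plasma equivalent zavegepant concentration by microsampling using the Tasso-M20 will be calculated by dividing with the individual B/P ratio". Protocol 4.2 speaks of "determining the blood-to-plasma ratio value for each participant to convert the dried blood concentrations collected using Tasso-M20". Both use the singular. Neither says how the 1 h and 8 h ratios become one value, or whether each is used at its own time. Tasso-Plus is not converted.

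**Comparing.** Tasso and venous samples are paired at "30 minutes, 1, 2-, 4-, 8-, and 12-hour postdose" (SAP 2.3), so both ratio times are also paired times. SAP 6.1.1 says the correlations of "paired Tasso-M20 versus venous phlebotomy concentrations will be reported" and adds a Bland-Altman analysis for each device against venous sampling. It neither mentions the shared plasma result nor plans a comparison of M20 with venous whole blood.

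**Sizing.** Protocol 9.5: "With a sample size of 7 evaluable participants per each Tasso device, and 6 Tasso-venous paired PK samples collected", giving 42 points per device against a cited recommendation of 30 to 40.

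**The concern.** An agreement analysis assumes that the two methods are measured separately, so that an error in either one can appear as a difference. For M20 at 1 h and 8 h this does not hold, because the reference plasma value is also a factor in the converted value. If it reads high, the conversion raises the M20 value with it, and part or all of the disagreement disappears. If one averaged ratio serves all six times, the same error also moves that participant's other four converted values, where that plasma result is not the reference.

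The comparison is the primary purpose of the study, and the sample size rests on a count of pairs. A reader would take the 42 M20 pairs to be the same kind of evidence as the 42 unconverted Tasso-Plus pairs. A further consequence is that the planned M20 comparison mixes device error with conversion error. The whole-blood results that could separate them are already being assayed.

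**Working it through.** **Counts.**
- Plan's figure: 7 participants × 6 times = 42 pairs per device. This reproduces.
- M20 pairs sharing a plasma result: 7 × 2 = 14, and 14/42 = 33.3%.
- Remaining M20 pairs: 7 × 4 = 28, against the cited 30 to 40.

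**Algebra.** Let M(t), B(t) and P(t) be the M20 dried-blood, venous whole-blood and venous plasma results. The plasma equivalent is M(t)/(B/P).
- Time-matched ratio at 1 h or 8 h: [M(t) × P(t)/B(t)] / P(t) = M(t)/B(t). Plasma drops out.
- Geometric mean of the two ratios: P(t) enters the converted value to the power ½ and the reference to the power 1, so half of its log error cancels.

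**Example.** Suppose the 1 h plasma result reads 30% high and everything else is exact. The apparent M20/venous ratio at 1 h is:
- 1/1.3 = 0.77 with a ratio not built on that result;
- √1.3/1.3 = 0.88 with the mean ratio;
- 1.3/1.3 = 1.00 with the time-matched ratio.

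With the mean ratio, that participant's 0.5, 2, 4 and 12 h values are multiplied by √1.3 = 1.14.

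**Effect on the limits.** The documents give no assay error, so the log-scale error SDs s_M, s_B and s_P are assumptions. Errors are taken as independent and the true B/P as constant. The mean ratio is used at the four other times under both readings. Variances of the log difference are:
- 1 h and 8 h, time-matched: s_M² + s_B²
- 1 h and 8 h, mean ratio: s_M² + s_B²/2 + s_P²/2
- other four times: s_M² + s_B²/2 + 3s_P²/2

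Pooled variance = (2 × coupled + 4 × other)/6. Limits of agreement scale with the SD. Where two values are given, the first is time-matched and the second is the mean ratio.

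| s_M / s_B / s_P | SD at 1 h, 8 h | SD at other times | Narrower at 1 h, 8 h | Pooled SD | Pooled narrower than other times |
|---|---|---|---|---|---|
| 0.10 / 0.10 / 0.10 | 0.141 | 0.173 | 18% | 0.163 | 5.7% |
| 0.10 / 0.10 / 0.15 | 0.141; 0.162 | 0.221 | 36%; 27% | 0.198; 0.203 | 10.4%; 8.0% |
| 0.10 / 0.05 / 0.05 | 0.112 | 0.122 | 9% | 0.119 | 2.8% |

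First row worked: coupled 0.01 + 0.01 = 0.02; other 0.01 + 0.005 + 0.015 = 0.03; pooled (0.04 + 0.12)/6 = 0.0267, SD 0.163; 0.163/0.173 = 0.943.

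A simulation with equal CVs of 5%, 10% and 15% gave the same pooled ratio, about 0.94, at each CV. The correlation of the difference with the reference plasma error was -0.58 at the other times, -0.35 at 1 h and 8 h with the mean ratio, and 0.00 with the time-matched ratio.

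**The other 28 pairs.** Ratio error is common to a participant's pairs. At equal SDs of 0.10 the shared variance is (0.01 + 0.01)/2 = 0.01 out of 0.03, a within-participant correlation of 0.33.

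**The case against.** Several objections have force.

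- **Pooling.** The SAP plans Bland-Altman per device, not per time. The 9 to 36% narrowing at 1 h and 8 h is therefore not what would be reported; the pooled 3 to 10% is the relevant figure. This stands.
- **Benchmark.** The four other times carry ratio error of their own. Against an error-free conversion (variance s_M² + s_P²: SD 0.141, 0.180, 0.112), the SD at 1 h and 8 h is equal in the first and third scenarios and smaller only in the second. The pooled SD is larger in all three (by about 15%, 10 to 13% and 6%). So the limits cannot be called too narrow in an absolute sense, only narrower than at times where the reference lies outside the conversion.
- **Reading.** The singular wording favours one ratio per participant, hence half cancellation. The 36% and the 1.00 example need the less supported time-matched reading. Coupling exists under both.
- **Overlap with the remedy.** With a time-matched ratio, the planned 1 h and 8 h comparison already equals M20 against whole blood on the ratio scale. The added analysis would then relabel it correctly rather than bring new numbers. With an averaged ratio it is new.
- **Scale and safeguards.** The SAP does not specify log differences, so these percentages do not transfer directly to raw-scale limits. Grossly anomalous concentrations may be excluded under SAP 5.3.1.
- **Sampling time.** Protocol Table 2, as extracted, seems to put the second B/P sample under 6 h. The table may be broken and the SAP says 8 h. If 6 h applied, 7 of 42 pairs would be coupled.

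These limit the size of the effect. None removes the shared plasma result.

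**Conclusion.** The point holds, with modest consequences. In 14 of 42 M20 pairs the plasma reference is part of the value compared with it; 28 pairs are free of this. The count and the algebra need no assumption beyond the SAP's 1 h and 8 h times. The pooled 3 to 10% rests on assumed SDs of 0.05 to 0.15, independent errors and log differences.

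Three stronger readings are tempting, and the documents do not support them:
- **The 14 pairs are worthless.** They are not. An M20 bias against venous whole blood appears in them in full, under either ratio rule.
- **M20 agreement will be badly overstated.** The pooled effect is small, and the SAP tests no hypothesis and sets no margin, so no formal conclusion changes.
- **The study misses its sample-size target.** The protocol's 42 is arithmetically correct, and the documents attach no independence condition to the 30 to 40 points. The shortfall to 28 matters only if one wants that many pairs whose plasma reference lies outside their own conversion. Those 28 are not mutually independent either.

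**What to change.** For Tasso-M20:

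1. **SAP 6.1.1, device-only agreement.** Add correlation and Bland-Altman of M20 dried-blood against venous whole-blood concentrations at 1 h and 8 h (14 pairs), without conversion.
2. **SAP 6.1.1, plasma-equivalent agreement.** Keep the planned 42-pair analysis. Add a sensitivity analysis on the 0.5, 2, 4 and 12 h pairs (28 pairs).
3. **SAP 3.1.1.** State how the 1 h and 8 h ratios are combined and which ratio applies at each time.

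Converting the 1 h value with the 8 h ratio, and the reverse, is not recommended. The log differences would be m1 - b8 + p8 - p1 and m8 - b1 + p1 - p8 (m, b and p being the log errors), so all plasma error still cancels in their average. At equal SDs of 0.10 each has SD √(0.01 + 0.01 + 0.02) = 0.200, against 0.173 at the other times, and their correlation is -0.02/0.04 = -0.5. The swap also relies on B/P being the same at both times.

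**Cost.** SAP wording and one extra table, with no new samples or assays. The 28-pair analysis is less precise and below the cited 30 to 40 points, so it should be labelled a sensitivity analysis.

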Abbreviation: AUC_{inf} = area under plasma concentration-time profile from time 0 extrapolated to infinite time; AUC_{last} = area under the plasma concentration-time profile from time 0 to the time of the last quantifiable concentration (C_{last}); CL/F = apparent clearance; C_{max} = maximum plasma concentration; $t_{1/2}$ = terminal half-life; TEAE = treatment-emergent adverse event; T_{max} = time to C_{max} ; V_z/F = apparent volume of distribution

Overall Design:

Brief Summary

This is a Phase 1, non-randomized, open-label study in healthy participants to primarily characterize the PK profile of IN zavege pant from samples collected using Tasso Devices (Tasso-Plus, for liquid blood sample collection and Tasso-M20, for dried blood sample collection) compared to standard venous phlebotomy. Leveraging these data will establish a correlation between the 2 methods and meet regulatory expectations before implementing these patient-centric blood collection devices in future studies. This study consists of 2 periods.

In period 1, 50% (n=7) of the enrolled participants will use Tasso-Plus, and the other 50% (n=7) will use Tasso-M20 to ensure having adequate PK data collected from each device. For each participant, PK samples will be collected after zavege pant administration in period 1 using the assigned Tasso device simultaneously with collecting venous blood samples. In addition, taste assessments will be performed at time intervals of 1 (immediately after dosing), 5, 10 and 20 minutes after zavege pant IN administration. Also, if feasible, 4 Japanese participants will be enrolled among those 14 participants to evaluate the PK and safety of zavege pant IN in Japanese vs. non-Japanese participants.

In period 2, a butterscotch candy will be given 5 minutes before administering the zavege pant IN study intervention. Taste assessment will also be performed after zavege pant IN administration with a butterscotch candy in period 2. For taste assessment, each participant will record the sensory attributes at timed intervals of 1 (immediately after dosing), 5, 10 and 20 minutes after zavege pant administration in each period.

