2.1. Study Rationale

As a component of zavegeptan clinical development, future pediatric studies will be conducted to evaluate the safety, tolerability, and PK of zavegeptan in participants 6 to less than 12 years of age with migraine. Recruiting and retaining pediatric patients in clinical trials has always been challenging due to a variety of factors, including inconvenience with patient preferences. To overcome some of those challenges, it is essential to prioritize patient-centric approaches that cater to the unique needs of pediatric patients. One such approach is PCS, which aims to reduce the burden on pediatric patients by minimizing the volume of the biological samples required and being less invasive with minimal pain compared to the venous phlebotomy collection method, which is particularly beneficial for pediatrics who are fearful of needles. Additionally, PCS offers greater flexibility to pediatric patients and their families by allowing at-home sample collection for those who may have difficulty traveling to clinics.

To allow the use of PCS in zavegeptan pediatric studies, a bridging or comparative study comparing the PCS approach with an equivalent conventional sampling technique is needed as a regulatory expectation to demonstrate the concordance of data from PCS in a controlled environment prior to implementation in large-scale clinical trials. Therefore, the primary objective of this study is to establish the correlation between zavegeptan concentration from samples collected using PCS devices compared to conventional venous blood sampling. In addition, if feasible, this study will also determine the PK and safety of zavegeptan IN in Japanese participants.

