To allow the use of PCS in zavegeptant pediatric studies, a bridging or comparative study comparing the PCS approach with an equivalent conventional sampling technique is needed as a regulatory expectation to demonstrate the concordance of data from PCS in a controlled environment prior to implementation in large-scale clinical trials.³⁶ Therefore, the primary objective of this study is to establish the correlation between zavegeptant concentration from samples collected using PCS devices compared to conventional venous blood sampling. PK sampling time points and duration, as described in [SoA, Table 2](#), were selected to adequately capture the rapid absorption of zavegeptant, since it has a T_{max} of 0.54 hours, as well as zavegeptant elimination phase. Based on zavegeptant PK data, zavegeptant has an elimination half-life of ~ 3 hours and an effective half-life of 6.55 hours following a single zavegeptant 10 mg IN dose. For Tasso bridging analysis, having PK samples that covers zavegeptant relevant concentration up to 12 hours will be sufficient to have adequate concentration-time comparison between the 2 methods. While for the Japanese participants, having PK timepoints up to 24 hours will cover >3 half-lives, which will be sufficient to adequately estimate zavegeptant half-life in Japanese. That's why 24 hours PK samples will only be requested for Japanese enrolled participants, as described in [SoA, Table 2](#).

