3.1.2. Zavegepant PK Parameters

Zavegepant PK parameters from samples collected using Tasso and venous phlebotomy will be derived from the concentration-time profile using non-compartmental methods, as detailed in Table 2. Actual PK sampling times will be used in the derivation of PK parameters. In the case that actual PK sampling times are not available, nominal PK sampling time will be used in the derivation of PK parameters.

Table 2. Definitions of PK Parameters

Parameter	Definition	Method of Determination
C_{max}	Maximum plasma concentration	Observed directly from data
AUC_{last}	Area under the plasma concentration-time profile from time 0 to the time of the last quantifiable concentration (C_{last})	Linear/Log trapezoidal method
AUC_{inf}^a	Area under the plasma concentration-time profile from time 0 extrapolated to infinite time	$AUC_{last} + (C_{last}/k_{el})$, where C_{last} is the predicted plasma concentration at the last quantifiable time point estimated from the log-linear regression analysis
T_{max}	Time for C_{max}	Observed directly from data as time of first occurrence
$t_{1/2}^a$	Terminal half-life	$\log_2(2)/k_{el}$, where k_{el} is the terminal phase rate constant calculated by a linear regression of the log-linear concentration-time curve
CL/F^a	Apparent clearance	Dose/ AUC_{inf}
V_z/F^a	Apparent volume of distribution	Dose/($AUC_{inf} \times k_{el}$)

a. If data permits.

PK parameters from samples collected using Tasso-M20 will be adjusted for B/P ratio.

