6.1.2. Zavegepant PK Parameters

The PK parameters of zavegepant will be listed and summarized descriptively for each collection method (Tasso-Plus, Tasso-M20 and venous phlebotomy), and by race (non-Japanese and Japanese), as data permits for the PK Parameter Analysis Set. Each zavegepant PK parameter will be summarized including the set of summary statistics as specified in Table 3.

For AUC_{last} , AUC_{inf} , and C_{max} , box and whisker plots for individual participant parameters will be constructed for each collection method and overlaid with geometric means.

Table 3. PK Parameters to be Summarized Descriptively by Collection Method and Race

Parameter	Summary Statistics
AUC_{inf} , AUC_{last} , C_{max} , CL/F , V_z/F	N, arithmetic mean, median, SD, %CV, minimum, maximum, geometric mean and geometric %CV
T_{max} , T_{last}	N, median, minimum, maximum
$t_{1/2}$	N, arithmetic mean, median, SD, %CV, minimum, maximum

Supporting data from the estimation of $t_{1/2}$ and AUC_{inf} will be listed by collection method and by race: terminal phase rate constant (k_{el}); goodness of fit statistic from the log-linear regression (r^2); the percent of AUC_{inf} based on extrapolation ($AUC_{extrap}\%$); and the first, last, and number of time points used in the estimation of k_{el} . This data may be included in the clinical study report.

For the Tasso vs. Venous comparison, natural log-transformed zavegepant AUC_{inf} (if data permit), AUC_{last} and C_{max} will be analyzed using a mixed effect model with blood collection method as fixed effect and participant as random effect. Estimates of the adjusted mean differences (Test – Reference) and corresponding 90% CIs will be obtained from the model with Venous as the Reference group and Tasso-M20 (or Tasso-Plus) as the Test group. The adjusted mean differences and 90% CIs for the differences will be exponentiated to estimate the adjusted geometric means ratio (Test/Reference) and 90% CIs for the ratios.

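### Tasso-M20 is compared with venous plasma only after conversion by each participant's own venous blood-to-plasma ratio; a pooled-ratio sensitivity run would show the agreement to expect without a paired venous draw

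*SAP*

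**What the plan says.** SAP 3.1.1 forms B/P ratios for each individual from venous whole blood and venous plasma at 1 h and 8 h on Day 1, and then states: "The plasma equivalent zavegepant concentration by microsampling using the Tasso-M20 will be calculated by dividing with the individual B/P ratio". Tasso-Plus is not converted. SAP 3.1.2 adds: "PK parameters from samples collected using Tasso-M20 will be adjusted for B/P ratio". Protocol 4.2 describes the same intention, "determining the blood-to-plasma ratio value for each participant to convert the dried blood concentrations", with the aliquot taken from the venous PK draw.

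Three M20 outputs use the converted values:

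- the correlation with venous concentrations (SAP 6.1.1);
- the agreement limits, where "Bland-Altman plot analysis will be performed for each pair to evaluate the bias and SD of the bias between the mean differences", with no measurement scale stated (SAP 6.1.1);
- the GMRs with 90% CIs, "with Venous as the Reference group and Tasso-M20 (or Tasso-Plus) as the Test group" (SAP 6.1.2).

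No pooled or fixed ratio, and no sensitivity analysis on the ratio, appears in SAP section 6, SAP Appendix 1 or the protocol. No hypothesis is tested and no agreement criterion is set.

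On purpose, the protocol synopsis says the data will "meet regulatory expectations before implementing these patient-centric blood collection devices in future studies". Section 2.1 motivates patient-centric sampling partly by "allowing at-home sample collection for those who may have difficulty traveling to clinics".

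**The concern.** A participant's own B/P ratio can be formed only when a venous sample is drawn from that participant. Dividing by it removes the participant's B/P level from the M20-venous difference, so the spread of B/P between people cannot appear in any planned M20 output. If M20 is later used alone, some common ratio would have to serve, and that spread would return as error. The documents do not say how M20 values would then be converted.

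With no acceptance limit in the plan, readers will judge M20 on its limits, GMR intervals and correlation. All three depend on the conversion, and only the one that needs a venous draw is planned. What is at stake is any inference from this study to M20 sampling without venepuncture. The device-versus-vein comparison itself is not in question.

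**Working it through.** **The plan's own figure.** 7 participants x 6 paired samples = 42 pairs per device (protocol 9.5). This reproduces. No power calculation applies.

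**Inputs from the documents.** Pairs at 0.5, 1, 2, 4, 8 and 12 h; ratios at 1 h and 8 h (SAP 3.1.1); 7 M20 users; ratios calculated for every individual, so 14 participants can supply a pooled value.

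**Assumptions, not in the documents.** Independent log-scale error with SD s on each M20, venous blood and venous plasma value; between-participant log SD t of the B/P ratio; B/P constant within a participant; the two log ratios averaged; Bland-Altman on the log scale.

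**Individual ratio.** The error is M20 minus mean log ratio minus plasma.

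- At the four times without a ratio: s² + s² + s² = 3s².
- At 1 h and 8 h the comparator plasma value is also in the ratio, which leaves 2s².
- Mean variance = (4 x 3s² + 2 x 2s²)/6 = 2.67s², so SD = 1.63s. It contains no t.

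**Pooled ratio, leaving out the participant being converted.** Variance = 2s² + t² + (t² + s²)/13.

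**Crossover.** Setting the two equal gives (0.667 - 0.077)s² = 1.077t², so t = 0.74s. Above this the pooled limits are wider; below it they are narrower, because an individual ratio rests on only two noisy values.

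**95% ratio limits, exp(±1.96 SD):**

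| s | t | SD individual | SD pooled | Limits individual | Limits pooled |
|---|---|---|---|---|---|
| 5% | 10% | 0.082 | 0.126 | 0.85-1.17 | 0.78-1.28 |
| 5% | 20% | 0.082 | 0.220 | 0.85-1.17 | 0.65-1.54 |
| 10% | 10% | 0.163 | 0.178 | 0.73-1.38 | 0.71-1.42 |
| 10% | 20% | 0.163 | 0.253 | 0.73-1.38 | 0.61-1.64 |
| 15% | 5% | 0.245 | 0.222 | 0.62-1.62 | 0.65-1.55 |

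A separate simulation (CVs as inputs, ordinary SD of the 42 differences) agrees. At assay CV 5% and B/P CV 20% it gives 0.86-1.17 against 0.66-1.51. Its individual-ratio limits stay at about 0.85-1.17 for every B/P CV from 0 to 30%.

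**AUC GMR, 90% CI, 7 participants (paired log differences, 6 df).** Multiply/divide factors, individual against pooled: 1.04 vs 1.17 (s 5%, t 20%); 1.08 vs 1.09 (10%, 10%); 1.12 vs 1.08 (15%, 5%). The GMR itself stays near 1 in the simulation.

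**Correlation.** With the elimination half-life of about 3 h from protocol 4.2, s 5% and t 20%, the log-scale correlation is 0.997 vs 0.977 (assumed between-participant concentration SD 0.2). The separate simulation, with SD 0.5, gives 0.997 vs 0.982. This is the least sensitive of the three outputs.

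**Precision of the pooled run.** At s 5%, t 20% the simulated pooled log SD from 7 users has a 5th-95th percentile range of about 0.12 to 0.30. The upper limit could therefore fall anywhere from exp(1.96 x 0.12) = 1.27 to exp(1.96 x 0.30) = 1.80.

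**The case against.** The case against is substantial. The individual ratio is chosen openly in protocol 4.2, and the SAP implements it faithfully. The same section limits the aim to a study that will "demonstrate the concordance of data from PCS in a controlled environment prior to implementation in large-scale clinical trials". The plan makes no statement about M20 without venous sampling, and at-home collection is described for patient-centric sampling in general, not for M20. The pooled run is imprecise with 7 users, and much of its information lies in the B/P mean and SD from all participants. It could also be run later from the same data, and a healthy-adult ratio does not answer the question for children.

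Most of this stands, and it makes the point an improvement and not a correction. It does not remove the point. The study is justified by later use that reduces venous sampling, and prespecifying the second conversion prevents a choice between conversions after the results are seen.

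Three stronger readings are tempting and are not supported:

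- That the plan overstates M20 agreement. The direction depends on t relative to s, and the documents give neither.
- That the correlation drops sharply. A log-scale fall from 0.99 to 0.91 (s 5%, t 20%) appears only if 6.55 h is used as the decline rate. Protocol 4.2 calls that figure the effective half-life.
- That the protocol and SAP contradict each other on B/P times. In the text copy of protocol Table 2 the second mark sits under 6 h, while the SAP says 8 h. The Day 2 header of that table is displaced by one column in the same direction, so this is a cell to check and not an established error.

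**Conclusion.** The point holds as a cheap, worthwhile addition and not as an error. The planned M20 limits and GMR intervals, and to a lesser degree the correlation, carry no between-participant B/P variation. They therefore answer the device-versus-vein question but not the question of M20 without a paired venous draw. That second use is an assumption consistent with the rationale. The gap may be large (s 5%, t 20%), negligible (10%, 10%) or reversed (15%, 5%). The documents do not allow a choice among these, which is the reason to measure it. Tasso-Plus is unaffected.

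**What to change.** 1. Keep the individual-ratio analysis as primary. In SAP 6.1.1 and 6.1.2 add one sensitivity run of the M20 Bland-Altman limits, GMRs and correlation. Use the geometric mean B/P ratio over all participants with B/P samples, leaving out the participant being converted. Use the same Bland-Altman scale in both runs.
2. Report the geometric mean and between-participant SD of B/P from all participants.
3. State that the pooled result rests on 7 M20 users and is imprecise, and that a healthy-adult ratio is not shown to hold at 6 to less than 12 years. Any statement about M20 without venous sampling should cite the pooled run.

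Housekeeping, not support for the point: say in SAP 3.1.1 how the 1 h and 8 h ratios are combined and what is done if one is missing. Check the second B/P mark in protocol Table 2 against the original, and reconcile it with the SAP if it differs.

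The cost is a few sentences and one extra run on samples already planned. The downside is that M20 agreement may look less favourable.
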